1.4.3 Pharmacodynamics

The pharmacodynamics (PD) of H3K27 methylation in the pediatric population has not previously been studied, however the inhibition of H3K27me3 has been demonstrated to be necessary for tazemetostat efficacy in nonclinical models. Preliminary PD data from peripheral blood monocytes (PBMs) demonstrated a relationship between Cycle 1, Day 15 tazemetostat exposure and H3K27me3 levels, with consistent and significant post-dose reductions in H3K27me3 observed at the 900 and 1200 mg/m² doses.

1.5 Rationale

1.5.1 Study Rationale

The clinical benefit of tazemetostat has not yet been established for pediatric subjects. This study will identify an RP2D for tazemetostat in pediatric subjects and characterize the safety profile and PK in this population. As there is a reasonable expectation based on nonclinical data and the Phase 1 experience in adults that clinical activity may be observed in children with INI1- and SMARCA4-negative tumors and synovial sarcoma, subjects will be carefully monitored for tumor response and symptom relief in addition to safety and tolerability.

1.5.2 Dose Rationale

1.5.2.1 Starting Dose for Escalation

Physiologically based PK modeling of the existing adult exposure data obtained in the FTIH study E7438-G000-101 informed the selection of the starting dose for this pediatric study. Systemic exposure data in adults together with in vitro data on the absorption, distribution, metabolism, and elimination (ADME) of tazemetostat were used to build a PK model that accurately described the time-concentration data from adults. This model was then transformed accounting for known age and developmental changes in physiological parameters, such as organ size and blood flows, as well as biochemical factors, e.g., the maturation of drug metabolizing enzyme expression and activity, to derive a series of age-based pediatric models for the PK of tazemetostat.

Tazemetostat doses that resulted in predicted AUC at steady-state (AUC_{ss}) within the range of values observed in adults were identified. For children 1 year to 18 years of age, the starting dose of 240 mg/m²/dose BID is predicted to result in 64% and 36% of the AUC_{ss} observed for adults at 800 mg/dose and 1600 mg/dose, respectively (based upon free base). For children 6 months to 1 year of age, the starting dose of 240 mg/m²/dose BID was predicted to result in 80% and 45% of the AUC_{ss} observed for adults at 800 mg/dose and 1600 mg/dose respectively. The 1600 mg/dose, which did not meet protocol-specified criteria for the MTD, is the highest dose level administered in the adult FTIH study, E7438-G000-101.

Preliminary PK parameters from the 240 mg/m² BID and 300 mg/m² BID dose cohorts in Study EZH-102 were determined and are displayed in [Table 2](#), which follows.

Table 2. Preliminary Geometric Mean (CV%) PK Parameters from Subjects 1 to 18 Years of Age in the 240 mg/m² BID Through 1200 mg/m² BID Dose Cohorts in Study EZH-102

Dose mg/m ² BID	Cycle 1 Day	n	C _{max} ng/mL	T _{max} ^a h	AUC ₍₀₋₈₎ ^b ng•h/mL	AUC ₍₀₋₂₄₎ ^c ng•h/mL
240	1	8	538 (72.7)	1 (1 – 4)	1360 (50.3)	NC
	15	7	324 (95.4)	2 (1 – 4)	935 (74.1)	2020 (74.9)
300	1	6	444 (50.5)	1 (1 – 2)	1330 (96.9)	NC
	15	5	357 (91.7)	1 (1 – 2)	1100 (101)	2370 (103)
400	1	6	711 (108)	1.5 (1 – 4)	2120 (69.0)	NC
	15	6	563 (211)	1 (1 – 4)	1680 (141)	3610 (134)
520	1	7	1900 (73.3)	2 (1 – 4)	7300 (85.8)	NC
	15	6	2130 (20.8)	1 (1 – 2)	5870 (34.4)	12,500 (35.1)
700	1	6	1830 (101)	1.5 (1 – 4)	6650 (104)	NC
	15	6	1150 (63.9)	1 (1 – 4)	3660 (52.1)	8140 (65.6)
900	1	6	4380 (35.8)	1.5 (1 – 2)	14,300 (33.7)	NC
	15	5	2380 (52.0)	2 (2 – 4)	9810 (33.3)	21,000 (32.6)
1200	1	6	1950 (61.4)	2 (2 – 8)	6640 (85.2)	NC
	15	6	3860 (31.6)	2 (1 – 2)	13,900 (38.2)	29,700 (43.9)

Abbreviations: BID= twice daily, C_{max}= maximum plasma concentration, T_{max}= Time to maximum concentration, AUC=Area under the concentration-time curve.

^aMedian (range) T_{max}

^bLast PK blood sample collection time point = 8 h

^cAUC₍₀₋₂₄₎ on Day 15 calculated as AUC₍₀₋₁₂₎ × 2

NC = not calculated

In children 1 to 18 years of age, the mean AUC₍₀₋₂₄₎ and C_{max} on Day 15 did not increase in a dose-proportional fashion at each dose level. There was an apparent trend for mean AUC₍₀₋₂₄₎ and C_{max} on Day 15 to increase in a greater than dose-proportional fashion when the tazemetostat dose increased from 240 mg/m² BID to 1200 mg/m² BID. The mean AUC₍₀₋₂₄₎ after administration of tazemetostat 1200 mg/m² BID is greater than the AUC₍₀₋₂₄₎ observed from the 50 mg/kg day dose group in which thymic lymphoma was observed in a single female rat in the 18-week toxicity study conducted in juvenile rats (18,500 ng•h/mL). However, the mean AUC₍₀₋₂₄₎ after administration of tazemetostat 1200 mg/m² BID is approximately 4-fold less than the AUC₍₀₋₂₄₎ from male rats in the 150/300 mg/kg day dose group (125,000 ng•h/mL) in which the incidence of thymic lymphoma appeared to increase to 4 of 21 animals in the 18-week toxicity study conducted in juvenile rats. (For more information on the results from the 13-week see Section 1.6.1.)

1.5.2.2 Determination of the Recommended Phase 2 Dose (RP2D) for Expansion

The Clinical Safety Review Committee (CSRC) convened on 06-Jul-2017 to review safety and PK from subjects at the 1200 mg/m² dose level. The mean AUC₍₀₋₂₄₎ after administration of tazemetostat 1200 mg/m² BID was 29,700 ng•h/mL was approximately 2-fold greater than the mean AUC₍₀₋₂₄₎ after administration of the highest dose evaluated dose (1600 mg BID) in adult subjects in Study E7438-G000-101 (15,400 ng•h/mL). No DLTs were observed at 1200 mg/m² dose level. Although the Rolling 6 statistical design supported the escalation to the next dose

level of 1600 mg/m², elevated chloride levels were observed in 3/6 evaluable subjects in the 1200 mg/m² dose level, and at previous dose levels as well. As tazemetostat is formulated as a hydrobromide salt, it was considered that the hyperchloremia could be an artifact of elevations in serum bromide. Thus, bromide levels were evaluated in two of five subjects on active treatment and were found to be elevated, though without any associated clinical signs or symptoms of neurologic toxicity associated with bromism. The CSRC reviewed data demonstrating a PK:PD relationship between Cycle 1 Day 15 tazemetostat exposure and H3K27me3 levels in PBMs consistent and significant post-dose reductions in H3K27me3 at the 900 and 1200 mg/m² doses. Given the occurrence of elevated bromide levels, as well as the PD data, a decision was made by the CSRC to proceed to the dose expansion phase of the protocol with the putative RP2D determined to be 1200 mg/m² BID dose level with the understanding that bromide levels as well as clinical signs and symptoms of bromide toxicity would be closely monitored in all newly and currently enrolled subjects receiving tazemetostat with guidelines for immediate dose reduction as indicated.

In this pediatric clinical study, subjects in dose escalation cohorts received BID oral treatment every day. For new patients with ATRT or any INI1-negative tumors with CNS involvement, the starting dose will remain 1200 mg/m² BID. For new patients that are non-ATRT, the starting dose will be 520 mg/m² BID (See Section 5.3). However, Cohorts 1 and 4 are now closed to enrollment.

[figure not shown]
As older subjects may prefer to take tazemetostat administered as tablets rather than as an oral suspension, the exposure of tazemetostat administered as tablets in subjects aged 10 years and older was explored in Cohort 4. However, Cohort 4 is now closed to enrollment. The bioavailability of tazemetostat administered as tablets is not expected to be greater than that of tazemetostat when administered as a suspension. Therefore, the safety profile of tazemetostat is expected to be similar when equal doses of tablets and suspension are administered. Due to concerns about tablet burden, subjects in Cohort 4 received tazemetostat 800 mg/m² TID (2400 mg/m²/day equivalent to 1200 mg/m² BID).

Tazemetostat may be administered, assuming subject and/or parent/guardian and Investigator consent, until disease progression (treatment failure) or unacceptable toxicity occurs.

1.6 Benefit: Risk Assessments

1.6.1 Animal Toxicology

Nonclinical safety assessments of tazemetostat included in vitro and monkey safety pharmacology studies, genotoxicity studies, and single- and repeat-dose toxicity studies in Sprague-Dawley rats and cynomolgus monkeys of 4- and 13-weeks duration. No notable cardiovascular, central nervous system (CNS), or respiratory risks were identified in nonclinical safety pharmacology assessments. Tazemetostat was not genotoxic in standard in vitro and in vivo assays. CCI

CCI [REDACTED]

CCI [REDACTED]

These studies were conducted in rats that, at initiation of dosing, were approximately 8 weeks old (adolescent rats; standard for support of dosing in adult patients) or 7 days old (juvenile rats; to support dosing of pediatric patients). CCI was not observed in 4-week studies in adolescent or juvenile rats. A brief summary of data from the 13-week studies is provided below in Table 3.

Table 3 Key Findings in 13-Week Rat Studies With Tazemetostat

Study Number	Age of rats at start of study	Tazemetostat doses mg/kg/day	CCI [REDACTED]
K14009	~8 week old adolescent rats	100 300 600	[REDACTED]
WIL-154506	Post-natal day 7 juvenile rats	50, 100 150/300 ¹ 150/600	[REDACTED]

¹ Rats in the 2 highest dose groups were dosed at 150 mg/kg/day from post-natal day (PND) 7 to PND 21 and escalated to 300 or 600 mg/kg/day thereafter to mitigate acute intolerability noted at very young ages in a previous dose range-finding rat study (WIL-779008) and to ensure adequate exposure.

² Group denominator includes main and recovery animals.

³ Group denominator also includes toxicokinetic animals if sacrificed early or found dead due to CCI [REDACTED].

Steady-state exposures (AUC from 0 to 24 hours [AUC₀₋₂₄]) in rats at the lowest dose (100 mg/kg/day) at which no CCI occurred in the 13-week adolescent rat study were 2.5- to 8-fold greater than that observed in humans at the recommended Phase 2 dose (RP2D; 800 mg twice daily [BID]) from the ongoing Phase 1/2 Study E7438-G000-101. In male juvenile rats, CCI was not seen at 50 mg/kg/day (AUC_(0-24h)=6340 ng•h/mL). A low incidence of CCI (2/60) was seen at AUC_(0-24h) 18,500-67,200 ng-h/mL and greater for juvenile rats, with higher incidence at AUC_(0-24h) 125,000- 290,000 ng-h/mL The first incidence of CCI in juvenile rats occurred at a similar AUC_{0-24h} as the single pediatric patient that developed CCI on Study EZH-102. There have been no cases of CCI in any adult patient given tazemetostat.

All patients will be actively monitored for signs or symptoms of abnormal bone formation during the trial. No incidences of new abnormal bone formation have been observed in the ongoing clinical study.

Female subjects of reproductive age will provide blood and urine samples for pregnancy testing at screening. All subjects must agree to use a reliable birth control method during and after the study as described in Section 8.5.11.

Additional animal toxicology is provided in the Investigator's Brochure (IB) for tazemetostat.

1.6.2 Hydrobromide Salt Formulation

An analysis of chloride levels in subjects on Study EZH-102 at the 1200 mg/m² dose level showed elevated chloride levels (beyond the ULN) in 5/7 subjects who had been treated at this dose level. Reviewing this finding further, subjects at lower dose levels (4/6 subjects at 900 mg/m², 4/6 subjects at 700mg/m² and 4/6 subjects at 520 mg/m²) also demonstrated elevated chloride levels.

Hyperchloremia is considered an artifact resulting from interference of serum bromide with the serum chloride assay (tazemetostat is a bromide salt). Artificially elevated serum chloride was also noted in repeat-dose nonclinical toxicology studies of tazemetostat in rats and monkeys at tazemetostat doses up to 1000 mg/kg/day. Ion exchange chromatography showed increased serum chloride in these nonclinical studies to be pseudo-hyperchloremia, representing increased bromide. Bromide levels were measured in the Phase 1 study of tazemetostat in adults. Bromide was within normal levels (<6.2 mmol/L) for all subjects taking the oral tablet formulation in doses up to 1600 mg BID. However, mean tazemetostat AUC₍₀₋₂₄₎ in children at the 1200 mg/m² dose level exceeded that observed in the 1600 mg BID dose group in adults from Study E7438-G000-101. Therefore, the assessment of bromide levels was instituted in Amendment No. 5 for all active and new subjects. Refer to Section 8.5.10 and Table 11 for the schedule of bromide level assessments and to Section 6.5.2 for dose modifications due to bromide toxicity. The chloride assay is being collected locally at every visit as part of the electrolyte panel, which is included in the standard blood chemistry assessment (Table 11).

For more details, refer to the tazemetostat Investigator's Brochure, Version 10.0.

1.6.3 Photo-Reactive Potential

There are nonclinical, in vitro data supporting a potential for phototoxicity, which has not been evaluated in humans. Hence, prolonged exposure to sunlight should be avoided during treatment. In addition, subjects should take other measures to avoid ultraviolet (UV) exposure such as wearing sunscreen and sunglasses, wearing protective clothing, and avoiding tanning beds. Refer to the tazemetostat Investigator's Brochure Version 10.0 for details.

1.6.4 CYP3A Metabolism

Tazemetostat is metabolized primarily by CYP3A and is a substrate for P-glycoprotein (P-gp). Therefore, treatment with strong inhibitors or strong inducers of CYP3A within 14 days prior to first dose of tazemetostat and for the duration of study treatment is prohibited. Tazemetostat was also shown to be a time-dependent CYP3A inhibitor and a CYP3A4 inducer (EC₅₀ value = 2.6 μmol/L) as well as an inhibitor of P-gp, CYP2D6, and the CYP2C family in vitro. P-gp, CYP3A, CYP2C8, CYP2C9, CYP2C19, and CYP2D6 substrates should be used with caution. Medications that are substrates for CYP3A, CYP2C8, CYP2C9, CYP2C19, or CYP2D6, and that have a narrow therapeutic range should be avoided if possible. For more details, refer to the tazemetostat Investigator's Brochure, Version 10.0.

1.6.5 Anticipated Safety Profile

This section summarizes the anticipated safety profile for tazemetostat based on the clinical experience in 90 pediatric subjects treated as of 24 May 2019 in this ongoing study (EZH-102), on nonclinical toxicology studies, and where noted, on 725 adult subjects treated with tazemetostat.

The following treatment-emergent AEs, regardless of causality, have been observed in $\geq 10\%$ of pediatric subjects in study EZH-102: vomiting, nausea, fatigue, diarrhea, and anemia.

The following nonserious adverse reactions to tazemetostat treatment have been observed in $\geq 2\%$ of pediatric subjects in study EZH-102: vomiting, nausea, fatigue, diarrhea, anemia, decreased appetite, constipation, thrombocytopenia, and neutropenia.

Tazemetostat treatment-related SAEs have been reported in 9 (10%) pediatric subjects in study EZH-102. The only serious adverse reaction reported in ≥ 1 pediatric subject has been decreased appetite (2 subjects).

The most common TEAEs that have led to interruption of tazemetostat dosing in pediatric subjects were: platelet count decreased (7%); hydrocephalus (6%); and thrombocytopenia, neutropenia, diarrhea, intestinal obstruction, dyspnea, hypoxia, and pyrexia (each 2%). The most common TEAEs leading to dose reduction in pediatric subjects have been platelet count decreased and thrombocytopenia, reported in 3 (3%) subjects and 2 (2%), respectively.

In addition, as described in Section 10.4, AESIs identified for the tazemetostat development program include: CCI /T-ALL, MDS, AML, and other myeloid malignancies like MPN. Epizyme considers the risk for CCI /T-ALL in tazemetostat clinical trials to be largely concentrated in pediatric patients. Myeloid malignancies have been reported in 5 of the 725 subjects in the adult population treated with tazemetostat. The risk of myeloid neoplasias as a result of EZH2 inhibition is considered uncertain based on available literature and Epizyme clinical data. Measures are in place to exclude potential subjects who may be predisposed to developing a myeloid neoplasia from participation in clinical studies and for early identification and monitoring of subjects who may be developing a myeloid neoplasia.

Further details of clinical study designs, tazemetostat exposure, and treatment-emergent AEs regardless of causality are outlined in the current IB.

Additionally, there are unknown risks of abnormal pregnancy outcomes and drug-drug interactions.

Based on the nonclinical toxicology of tazemetostat, the potential risks associated with treatment include CCI, bone changes, bile duct hyperplasia, lymphoid depletion, teratogenicity, and phototoxicity.

As per Section 1.6.2, there is a potential risk of bromide toxicity related to the hydrobromide salt used in the formulation of tazemetostat. Signs of bromide toxicity consist of CNS AEs including

lethargy, headache, ataxia, and coma. As described in Section 1.4.2 (clinical experience), bromide elevation was reported in 3 (3.3%) of 90 pediatric subjects as of 24 May 2019, all of which were considered to be related to tazemetostat treatment, but there were no AEs suggestive or indicative of bromide toxicity.

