14.5.3 Adverse Events

Treatment-emergent adverse events (TEAEs) are defined by applying treatment-emergent signs and symptoms (TESSs) philosophy. AEs will be regarded as TEAEs if one of the following conditions is met:

- Emerge after the time of the administration of the first dose, having been absent prior to the first dose.
- Re-emerge, having been present but stopped prior to the time of the administration of the first dose.
- Worsen in severity after the time of first dose administration relative to the pre-treatment state, when the AE is continuous.

An AE with partial or completely missing start date and/or time will always be assumed as TEAE, unless it can be determined to be “prior to administration” from the incomplete start date/time or resolution date/time (e.g., month, year is before first administration date, or resolution date is before date of first administration).

Only TEAEs will be summarized. Summaries of TEAEs will consist of the number and percentage of subjects reporting the AE by SOC and by PT. TEAEs which occur more than once for a subject will be counted only once in the subject frequencies. TEAEs with different CTCAE grades for a subject will be counted at the worst (highest) grade for the same SOC (likewise for PT). TEAEs with different drug relationship for a subject will be counted at strongest relationship for the same SOC (likewise for PT). TEAEs with missing relationship to study treatment will be counted as “related”. TEAEs with missing CTCAE grade will be counted as Grade 3 (“severe”).

Summaries of TEAEs by study cohort and overall will be produced to present the number and percentage of subjects with:

- Any TEAE
- Any treatment-related TEAE
- Any TEAE with CTCAE Grade 3 or higher
- Any TEAE leading to study treatment discontinuation
- Any Serious TEAEs
- Any TEAE of special interest

Listings will be provided for the following:

- AEs
- TEAEs leading to study treatment discontinuation
- Serious TEAEs
- Fatal TEAEs
- TEAEs of special interest

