17.1. ADVERSE EVENTS

Verbatim AEs terms will be coded using the Medical Dictionary for Regulatory Activities (MedDRA) version in effect at the time of the analysis. Summary tables will be based on treatment emergent adverse events (TEAEs) which are defined as AEs that started or worsened

in severity on or after the day of the first dose of study drug through 30 days after the end of study drug. Missing or partially missing start and end dates for AEs and SAEs will be handled according to the conventions described in Appendix A. For cases in which it is not possible to ascertain treatment-emergence, the event will be classified as treatment-emergent. All AEs, treatment emergent or otherwise, will be presented in subject data listings.

Each summary table will include the incidence (number and percentage) of subjects reporting any TEAE, as well as, by SOC and PT. A subject will be counted once within an SOC, even if the subject experienced more than one TEAE within a specific SOC (likewise for PT).

Investigator assessed severity grade will be based on the National Cancer Institute CTCAE, version 4.03. For summary purposes, TEAEs with a missing severity will be classified as missing. A subject will be counted once at the worst severity grade within a SOC and/or PT.

Investigator assessed causality to study drug will be categorized as “not related,” “unlikely related,” “possibly related,” or “related” to study drug. For summary purposes, treatment-related TEAEs will include events with relationship to study drug classified as “possibly related” or “related”. A TEAE with a missing causality will be classified as “possibly related” to study drug. A subject will be counted once at the strongest causality within a SOC and/or PT.

TEAEs of special interest are defined in Section 10.4 of the protocol. In consultation with study clinicians, this subset of TEAEs will be identified using MedDRA terms.

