An overview summary table of subjects with TEAEs will be provided by study part and overall and will include the number of subjects with any TEAE, any TEAE Grade 3 or 4, any TEAE DLT (as defined in the protocol Section 6.3), any treatment-related TEAE, any treatment-related TEAE Grade 3 or 4, any TEAE leading to dose reduction, any TEAE leading to study drug interruption, any TEAE leading to discontinuation of study drug, any TEAE leading to study discontinuation, any serious TEAE (TESAE), any treatment-related TESAE, any protocol defined TEAE of special interest. In accordance with the TEAE table presentation described above, AEs will be summarized by study part and overall as follows:

- TEAEs
- TEAEs with $\geq 10\%$ incidence overall based on PT
- TEAEs of grade 3 or 4
- Treatment-related TEAEs
- Treatment-related TEAEs of grade 3 or 4
- TEAEs leading to dose interruption
- TEAEs leading to dose reduction

- TEAEs leading to discontinuation of study drug
- TEAEs leading to discontinuation from study
- Treatment-emergent serious adverse events (SAEs)
- Treatment-related treatment emergent SAEs
- TEAEs of special interest
- DLTs

Additionally, separate listings of DLTs, SAEs, , TEAEs leading to discontinuation of study drug and TEAEs leading to dose modifications (interruption and dose reduction). A listing of TEAEs of special interest will be also provided.

Adverse events with CTCAE Grade 5 or outcome of death are excluded from AE summary tables and summarized under death related tables.

Deaths

Deaths will be summarized and listed as follows:

- Summary and listing of subjects who died during and till 30 days after last dose of study drug
- Summary and listing of subjects who died during and till 30 days after last dose of study drug with treatment-related TEAEs
- Summary and listing of subjects who died after 30 days after the last dose of study drug with treatment-related AEs

The summary and listing will include the reason for death:

- Any AE (by MedDRA preferred Term)
- Any treatment related TEAE
- Progression
- Tumor progression
- Disease under Study

- Unknown/Other causes

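### SAP 17.1 has no grouped term for low platelets, which this trial reports under two preferred terms, so the preferred-term rows of five TEAE tables may understate the event

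*Protocol*

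**What the plan says.** Protocol 1.6.5 describes the safety profile from "clinical experience in 90 pediatric subjects treated as of 24 May 2019". The leading causes of dose reduction are given as "platelet count decreased and thrombocytopenia, reported in 3 (3%) subjects and 2 (2%), respectively". For dose interruption the same section puts platelet count decreased first at 7%, then hydrocephalus at 6%, with thrombocytopenia among several terms at 2% each. Neither platelet term is in its list of TEAEs seen in at least 10% of children.

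SAP 17.1 fixes the layout of the AE tables: "Each summary table will include the incidence (number and percentage) of subjects reporting any TEAE, as well as, by SOC and PT". The counting rule is that "A subject will be counted once within an SOC", and the same applies to each PT. The table of common events takes TEAEs with at least 10% "incidence overall based on PT". SAP 17.1 also plans tables of treatment-related TEAEs, Grade 3 or 4 TEAEs, and TEAEs leading to interruption and to reduction, all in this layout. The only set of MedDRA terms it plans to assemble is for events of special interest, and the events of special interest named in protocol 1.6.5 do not include low platelets.

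Protocol 14.5.3 has the same counting basis: "Summaries of TEAEs will consist of the number and percentage of subjects reporting the AE by SOC and by PT". It does not itself plan interruption or reduction tables; those come from the SAP.

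**The concern.** Platelet count decreased and thrombocytopenia describe the same finding for the purpose of asking how often low platelets occurred or changed treatment. When a table has one row per PT and no row for the pair, a reader cannot recover the number of children affected. Adding the rows double-counts any child with both terms, and taking the larger row misses any child with only the other. An SOC row does not help, because it cannot isolate low platelets from the other events in its class.

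At stake is the description of the event that leads both dose-action lists in the protocol's own summary. Safety and tolerability is a secondary objective for all subjects. A cut applied to single PTs can also leave a common event out of the common-event table when its reports are divided between two terms.

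**Working it through.** **Inputs, all from protocol 1.6.5**
- Denominator: N = 90 children, data cut 24 May 2019.
- Dose reduction: platelet count decreased 3, thrombocytopenia 2.
- Dose interruption: platelet count decreased 7%, hydrocephalus 6%, thrombocytopenia 2% (percentages only).
- Number of children with both platelet terms: not given.

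**Reproducing the stated figures**
- Reduction: 3/90 = 3.3% and 2/90 = 2.2%, which round to the stated 3% and 2%.
- Interruption, taking N = 90: the only whole number that rounds to 7% is 6 (6/90 = 6.7%); to 6%, 5 (5/90 = 5.6%); to 2%, 2 (2/90 = 2.2%).

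**Unique children with either term**

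If a and b children have the two terms, the number U with at least one satisfies max(a, b) ≤ U ≤ a + b. The lower bound is full overlap and the upper bound is none.

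| Table | a | b | U | U/90 | Larger PT row alone | Possible shortfall |
|---|---|---|---|---|---|---|
| Reduction | 3 | 2 | 3 to 5 | 3.3% to 5.6% | 3.3% | 0 to 2 children |
| Interruption | 6 | 2 | 6 to 8 | 6.7% to 8.9% | 6.7% | 0 to 2 children |

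The shortfall is 0 to 2.2 percentage points (2/90) in each table.

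**The 10% cut**
- On 90 subjects the cut is 0.10 × 90 = 9 children.
- Interruptions with no overlap already give 8. One further child with low platelets but no interruption would bring the pooled event to 9/90 = 10%.
- Neither term is on the protocol's 10% list. If that list was built on single PTs (an assumption), each term occurred in at most 8 children. The interruption counts give floors of 6 and 2. The pooled incidence then lies between 6/90 = 6.7% (full overlap) and (8 + 8)/90 = 16/90 = 17.8% (no overlap). This is a bound, not an estimate, because the overall incidence of each term is not reported.

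**Ranking**

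Platelet count decreased alone is already first for interruption (6 children against 5 for hydrocephalus) and first for reduction (3). Pooling leaves the order unchanged.

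**Whether another planned output gives the missing count**
- SAP 17.2 laboratory tables: platelet count is a collected analyte (protocol 8.5.10), and its worst CTCAE grade is tabulated whatever PT was used. These tables carry no causality, interruption or reduction.
- SAP 17.1 overview and SAP 14.1 exposure summary: these count subjects with any event leading to a dose action, without the cause.
- DLTs (protocol 6.3): defined by CTCAE grade, bleeding and duration, so the split does not affect who has a DLT. They cover Cycle 1 of dose escalation only.
- SAP 17.1 listing of TEAEs leading to dose modification: a unique count could be made by hand for interruption and reduction, but this is not a planned incidence and does not serve the 10%, treatment-related or Grade 3-4 tables.

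**The case against.** The strongest reply is that nothing is in error. SOC-and-PT tabulation is consistent between protocol and SAP, the tables are descriptive, and no hypothesis, DLT or stopping rule depends on them. All AEs are listed, both platelet terms are already visible in the protocol's summary, and the study report could add a pooled row without amending the SAP. Much of this stands: no data are lost, and the consequence is one of presentation. What does not stand is that a later addition is equivalent. A grouping chosen after the counts are seen is a post-hoc choice, whereas one fixed before database lock is not.

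Several stronger readings are tempting, and the documents do not support them.
- **Low platelets are understated in every table.** The any-TEAE rows, the overview, the grade-based DLT determination and the laboratory shift tables are untouched.
- **Understatement is certain.** With full overlap it is zero, and overlap is not reported.
- **The protocol's lists already show the effect.** Absence from the 10% list does not show that the pooled event reached 9 of 90. The list of non-serious adverse reactions in at least 2% names thrombocytopenia but not platelet count decreased. Informal pooling or causality assessment could explain that, and the documents do not say which; pooling would point the other way.
- **The leading toxicity is disguised as minor events.** It ranks first under one term alone.
- **The same split affects neutrophils, hemoglobin and white cells.** Protocol 1.6.5 reports only neutropenia and anemia for these lines, so a split is documented for platelets alone.

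**Conclusion.** The point holds in limited form and is worth acting on. SAP 17.1 counts by SOC and single PT with no grouped low-platelet term, and this trial has used both PTs. The PT rows of the 10%, treatment-related, Grade 3-4, interruption and reduction tables may therefore understate low platelets. At the 2019 cut the size is 0 to 2 children of 90 in each dose-action table: 3.3% to 5.6% against 3.3% for reduction, and 6.7% to 8.9% against 6.7% for interruption. The pooled event could also reach 10% with neither PT in the common-event table; that is a possibility, not a finding.

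This rests on three assumptions: the interruption percentages use the 90-subject denominator; the two terms should be read as one event; and the overlap may lie anywhere between none and complete. The figures come from an interim summary, so they show that the split exists, not how large it will be in the final tables. Whether the two PTs share an SOC depends on MedDRA, which is not supplied, but the conclusion holds either way.

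**What to change.** In SAP 17.1, before database lock, pre-specify one grouped term: thrombocytopenia or platelet count decreased. Count each subject once, at worst grade and strongest causality. Show the grouped row in the five SAP tables (at least 10% incidence, treatment-related, Grade 3 or 4, leading to interruption, leading to reduction), and keep the two PT rows beneath it. Apply the 10% cut to the grouped row as well as to single PTs. State that the same rule extends to other cytopenias only if the coded data contain both forms of the term.

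The cost is a short term list and minor programming, with no new data. The reported low-platelet rate may become slightly less favourable.
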